5.3 Definitions of Events

- Airway maneuver: consists of either airway maneuvers such as chin lift, jaw thrust, , mask ventilation, or the insertion of a nasal or oral airway, supraglottic device, or ETT
- Oxygen desaturation: SpO₂ ≤ 90% for ≥ 15 seconds
- Cardiac complications is defined by a change in either SBP or DBP > 25% from baseline, a change in heart rate > 25% from baseline, arrhythmias, and ST-changes on EKG (ST depression or elevation).
- Full recovery is defined as the time from endoscope withdrawal until a MOAA/S score of 5 was achieved and the patient could drink liquids and ambulate independently.
- Full recovery until actual discharge is defined as the interval from full recovery until the patient exited the recovery room.
- Induction to full sedation is the time from initial administration of intravenous sedative or analgesic to the insertion of the endoscope
- Intra-procedural period was defined as the time of first scope insertion until the last scope removal.
- Procedural interruption is defined as the removal of the endoscope due to a respiratory complication
- Modified Observer's Assessment of Alertness/Sedation Scale (MOAAS) from 1 – 5

MOAAS:

- 0 No response after painful trapezius squeeze
- 1 Responds only after painful trapezius squeeze
- 2 Responds only after mild prodding or shaking
- 3 Responds only after name is called loudly and/or repeatedly
- 4 Lethargic response to name spoken in normal tone
- 5 Responds to name spoken in normal tone

5.4 Crossover to Other Group After Randomization

Patients in either Group A or Group B will be eligible for crossover to the other group at the discretion of the anesthesiologist in order to safely complete the procedure and minimize the likelihood of future adverse events.

Group A (Standard care with a facemask) to Group B (SuperNO₂VA™EtCO₂) group will occur when during the procedure either: 1) after insertion of an oral or nasal airway and hypoxia is persistent, and 2) before supraglottic airway endo tracheal tube insertion if the care team wishes.

Group B to Group A: If any of the following occur: 1) patient refusal to wear the mask once placed due to claustrophobia, poor fit or discomfort or any other reason; 2) if a nasal or oral airway is needed.

6. SUBJECT WITHDRAWALS

Subjects may be withdrawn from the study for the following reasons:

1. Unacceptable adverse events (safety or tolerability)
2. The subject's may withdraw from the study at any time and for any reason
3. Clinician decision that it is in the best interest of the subject to withdraw from the study

7. SAFETY AND REPORTABLE EVENTS

7.1 Adverse Event Definition

Adverse Event (AE): An Adverse Event is any undesirable clinical event occurring to the subject during clinical study, whether or not it is considered related to the investigational product. This includes a change in a subject's condition or laboratory results, which has or could have a deleterious effect on the subject's health or well-being. An Adverse Event that is related to the investigational device may be referred to as an Adverse Device Effect (ADE).

7.2 Adverse Events

For study conduct purposes, adverse events will be categorized at the investigative site into two groups: Serious Adverse Events, and Non-Serious Adverse Events. The Investigator as either related to the device or its deployment, or not related to the device or its deployment will assess the causal relationship of each adverse event. Each Adverse Event assessed as being related to the device or its deployment will also be assessed by the Investigator as being anticipated or unanticipated.

7.3 An adverse event does not include:

- Medical or surgical procedures; the condition that leads to the procedure is not an adverse event
- Pre-existing disease, conditions, or laboratory abnormalities present at the start of the study that do not worsen in frequency or intensity
- Situations where an untoward medical occurrence has not occurred (e.g., hospitalizations for cosmetic or elective surgery or social/convenience admissions)
- Expected ICU course

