7.4 Unanticipated Adverse Device Effect (UADE)

Any device related adverse event, the nature or severity of which is not consistent with or listed in the applicable product information (e.g., instructions for use, subject informed consent document, subject information brochure [if applicable], promotional literature) or any other unanticipated serious problem associated with a device that relates to the rights, safety, or welfare of subjects.

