7.5 Responsibilities for Reporting Serious Adverse Events

All adverse events, whether observed by the Investigator, elicited from or volunteered by the subject, should be documented. Each adverse event will include a brief description of the experience, the date,

of onset, the date of resolution, the duration and type of experience, the severity, the relationship to investigational product (i.e., drug or device), contributing factors, and any action taken with respect to the study drug/device.

Investigators and research coordinators will be instructed that all AE and corresponding relevant information should be recorded on the Adverse Event Form. In addition, the clinical site will be responsible for notifying Sponsor within 24 hours of any UADE. All relevant information regarding an UADE should be recorded on the Adverse Event Form and reported to Sponsor via Fax within 24 hours of the event. In addition to the event form, copies of adverse device effect related source documents should be forwarded to the Sponsor.

The Principal Investigator is responsible for reporting AEs to the IRB of record in accordance with IRB procedures. The Sponsor is responsible for informing the appropriate regulatory authorities and other Investigators of any UADEs that have occurred.

The Principal Investigator will record all serious adverse experiences that occur during the study period in the appropriate source documents and/or AE log as applicable.

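### Section 7.3 excludes from adverse events any condition that leads to a procedure, which contradicts section 7.1 and can leave in-study harms out of AE and SAE reporting and review

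*Combined protocol and SAP*

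**What the plan says.** Section 7.1 is broad: "An Adverse Event is any undesirable clinical event occurring to the subject during clinical study, whether or not it is considered related". Section 7.2 divides adverse events into serious and non-serious. Section 7.3 then lists four exclusions:

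- "Medical or surgical procedures; the condition that leads to the procedure is not an adverse event";
- pre-existing disease, conditions or laboratory abnormalities that do not worsen;
- "Situations where an untoward medical occurrence has not occurred", with elective or social admissions as examples;
- "Expected ICU course".

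Section 7.5 sets the recording duty: "All adverse events, whether observed by the Investigator, elicited from or volunteered by the subject, should be documented". It adds that the Principal Investigator "will record all serious adverse experiences that occur during the study period". No section defines a serious adverse event.

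Three bodies depend on these records. The IRB receives adverse event reports from the Principal Investigator (7.5). The DSMB looks at the primary endpoint and tabulated adverse events at the halfway mark (4.2, Planned Statistical Analysis). An anesthesiologist outside the study reviews adverse events, serious adverse events and deviations, and sees serious ones within 24 hours (Data Safety Monitoring).

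**The concern.** An in-study event that needs a procedure meets the definition in 7.1 and is struck out by the first exclusion in 7.3. A coordinator deciding whether to complete a form may well turn to the specific list before the general definition. Among otherwise similar events, one that needs no procedure would then be recorded, while one that does need a procedure might not be.

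What is at stake is the completeness of AE and SAE reporting, and of the material that the safety reviewers see. Harms that the plan collects nowhere else matter most, because the adverse event form is the only planned place for them.

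**Working it through.** No arithmetic applies. The plan states no expected rate of adverse events, serious adverse events, intubation or any procedural complication, so there is no figure to reproduce. The check compares the sections.

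**1. Can the first exclusion be read as covering only conditions present before enrolment?** Its wording sets no such limit. The second exclusion already deals with pre-existing conditions that do not worsen. If the first covered only those, it would add little beyond the procedures themselves. Its literal reach therefore includes events that arise during the study.

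**2. Does the rest of 7.3 support that reach?** No. The third exclusion removes situations in which nothing untoward happened, which implies that untoward occurrences are meant to count. The first exclusion is out of line with its neighbour as well as with 7.1.

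**3. Does the serious-event route recover these events?** Not reliably. Under 7.2 a serious adverse event is one category of adverse event, so a condition that is not an adverse event has no clear way to become a serious one. The duty in 7.5 to record serious adverse experiences points towards recording, but it rests on a term that the documents do not define.

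**4. Does the device-effect route recover them?** In part. The first limb of the definition in 7.4 requires a device-related adverse event. The second reaches "any other unanticipated serious problem associated with a device" without requiring an adverse event, but only if the problem is unanticipated. Section 8.1 names ocular injury as a recognised risk, so an ocular injury needing a procedure could be treated as anticipated and fall outside that limb.

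**5. Which harms are collected independently of the adverse event definition?**

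| Harm | Collected elsewhere? | Where |
|---|---|---|
| Airway maneuver, up to a supraglottic device or endotracheal tube, with reason and duration | Yes, compared between arms | Summary table; section 1; 5.3 |
| Oxygen desaturation | Yes, measured | 5.2; 5.3 |
| Removal of the endoscope for a respiratory complication | Yes, compared between arms | Summary table; section 1; 5.3 |
| Cardiac complications | Yes, compared between arms | Summary table; section 1; 5.3 |
| Ocular injury needing a procedure | No | Named only as a risk in 8.1 |
| Perforation, bleeding or aspiration needing a procedure (illustrative; not named in the plan) | No endpoint of its own | None |

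**6. Do the safety reviewers receive the separately collected items?** The plan does not say so. Besides adverse events, the DSMB is said to see the primary endpoint, and the independent anesthesiologist's review covers deviations and, at the interim, efficacy on the primary endpoint. That endpoint is the time to the first airway intervention, so it does not distinguish a chin lift from an endotracheal tube. As the plan is written, the severity of an event reaches these reviewers through the AE and SAE records.

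**The case against.** The strongest objection is that other text favours recording. Section 7.1 is broad, 7.5 asks for all adverse events and all serious adverse experiences, and the second limb of 7.4 does not depend on the adverse event definition. The plan also often uses the word procedure for the colonoscopy, so the excluded condition might be read as merely the indication for it. This stands to the extent that omission is a risk and not a certainty. It does not remove the defect: the item speaks of medical or surgical procedures generally, and a site could follow either reading.

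A reader might infer more, namely that the most serious airway harms vanish from the trial. Suppose, purely as an assumption, that 4 patients in one arm and 1 in the other needed an invasive airway. The adverse event table could show 0 versus 0. The airway maneuver comparison would still show 4 versus 1, with reasons. The documents therefore do not support a loss from the airway comparisons, and the plan names no single safety outcome from which such events could drop.

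Nor do they show that omission always rises with severity, since a grave event managed without a procedure stays in the count. A difference in omission between arms is possible but cannot be shown from the text.

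The ICU item might also be taken as a serious gap. If no ICU stay is expected in an outpatient colonoscopy trial, it excludes nothing, and no effect has been shown.

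**Conclusion.** The first exclusion in 7.3 is wrong as written and contradicts 7.1. The consequence is limited to AE and SAE reporting and to the reviews that rely on it. It does not touch the primary outcome, the sample size or the between-arm airway comparisons. It matters most for harms with no endpoint of their own.

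The size cannot be estimated. Among in-study events that need a procedure, the share left out could lie anywhere from none to all, depending on how the site reads the conflict, and the documents give no rate for such events. The conclusion assumes that staff may apply the list in 7.3 literally, and that no case report form instruction outside these documents overrides it.

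**What to change.** Reconcile 7.3 with 7.1 by replacing the first item with wording such as: *Medical or surgical procedures are not themselves adverse events; a condition that arises or worsens after enrolment and leads to the procedure is an adverse event.* Keep the separate item on unchanged pre-existing conditions. As tidying only, delete the ICU item, which has no evident role in a trial that excludes inpatients.

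The cost is two lines of protocol text, a note to site staff and a few more adverse event forms. A definition of serious adverse event would be a useful addition in the same amendment, because the 24-hour review depends on that term.

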7.4 Unanticipated Adverse Device Effect (UADE)

Any device related adverse event, the nature or severity of which is not consistent with or listed in the applicable product information (e.g., instructions for use, subject informed consent document, subject information brochure [if applicable], promotional literature) or any other unanticipated serious problem associated with a device that relates to the rights, safety, or welfare of subjects.

7.5 Responsibilities for Reporting Serious Adverse Events

All adverse events, whether observed by the Investigator, elicited from or volunteered by the subject, should be documented. Each adverse event will include a brief description of the experience, the date,

of onset, the date of resolution, the duration and type of experience, the severity, the relationship to investigational product (i.e., drug or device), contributing factors, and any action taken with respect to the study drug/device.

Investigators and research coordinators will be instructed that all AE and corresponding relevant information should be recorded on the Adverse Event Form. In addition, the clinical site will be responsible for notifying Sponsor within 24 hours of any UADE. All relevant information regarding an UADE should be recorded on the Adverse Event Form and reported to Sponsor via Fax within 24 hours of the event. In addition to the event form, copies of adverse device effect related source documents should be forwarded to the Sponsor.

The Principal Investigator is responsible for reporting AEs to the IRB of record in accordance with IRB procedures. The Sponsor is responsible for informing the appropriate regulatory authorities and other Investigators of any UADEs that have occurred.

The Principal Investigator will record all serious adverse experiences that occur during the study period in the appropriate source documents and/or AE log as applicable.

8. RISK/BENEFIT ASSESSMENT

8.1 Potential Risks

As with use of all medical devices, complications may occur. Recognized risks associated with the use of the study intervention include, but are not limited to, the following:

- Allergic reactions: although the materials being used are hypoallergenic and the risk is small, there remains a risk for an allergic reaction that may result in hives, swelling, or anaphylaxis.
- Ocular injury: although the SuperNO₂VA Et™ Mask was designed to contour away from the eyes, mishandling of the mask or accidental slippage from its intended position may result in contact with the subject's eye, resulting in a corneal abrasion and/or other ocular injury.
- Pressure ulcer: although the clinical protocols states to remove the SuperNO₂VA Et™ after successful placement of an invasive airway, if the SuperNO₂VA Et™ is mistakenly left on the subject for an extended period of time it can lead to a pressure ulcer.

8.2 Risks Minimization

- To minimize the risk of allergic reactions the SuperNO₂VA Et™ has undergone and successfully passed biocompatibility testing. However, there is still a very small risk for an allergic reaction that may result in hives, swelling, or anaphylaxis.
- To minimize the risk of an ocular injury, it is recommended that all clinicians be properly trained on how to use the SuperNO₂VA™EtCO₂ and be familiar with the Instructions For Use (IFU).
- To minimize the risk of a pressure, it is recommended that all clinicians be properly trained on how to use the SuperNO₂VA™EtCO₂, be familiar with the Instructions For Use (IFU), and monitor the subject's face for redness every 30 minutes that the SuperNO₂VA™ EtCO₂ is secured to the subject.

8.3 Potential Benefits to Subjects

- Improved oxygen delivery, administration, and oxygenation
- Potentially able to reduce post-op respiratory complications

8.4 Alternatives to Participation

The alternative for not participating in this study is not using the SuperNO₂VA™ EtCO₂ for gastrointestinal endoscopy.

9. CONFIDENTIALITY OF DATA AND INFORMATION STORAGE

All study participants will be assigned a study number. The PI will maintain the key to the study number and medical record number in a password locked UTH computer. Information about study subjects will be kept confidential and managed according to the requirements of the Health Insurance Portability and Accountability Act of 1996 (HIPAA). Patient data will be entered into a password protected electronic spreadsheet and online database (i.e. REDCap). Only the investigators, who have been invited to participate in the study and who are registered with the IRB, as well as have documented completion of all IRB and HIPAA regulations will have access to patient data, but not the medical record key.

Electronic records will be stored for 5 years after study conclusion on the institution's password protected computer, after which time they will be deleted. If there is a breach in confidentiality or violation of IRB and HIPAA regulations, the IRB will be notified in a timely manner (within 7 days) and appropriate actions taken thereafter. All data used in the analysis and reporting of this investigation will be de-identified.

In order to ensure compliance with the Health Insurance Portability and Accountability Act (HIPAA), all subjects enrolled in the study will be required to provide authorization to disclose Protected Health Information (PHI). This authorization will be included in the informed consent document as required by the IRB. In all study reports and in any resulting publications, subjects will not be referred to by their initials and/or study identification number.

The co-PIs will monitor for safety. Data safety will be ensured by having all patient consents and information stored in the REDCaps system. After randomization patient and study data outside the REDCaps system will only be identified by study number. Any recruitment data and randomization tables will be stored as a single copy in a locked cabinet in a PI's secured Faculty office.

10. SAMPLE SIZE DETERMINATION AND DATA ANALYSIS

10.1 Sample Size Determination

For sample size calculation we used the standard sample size calculation equation¹⁶:

$$n = \frac{2(Z_{\alpha} + Z_{1-\beta})^2\sigma^2}{\Delta^2}$$

σ = variation of the measurement

Δ = difference to be detected

σ and Δ are based on the outcome values from previous publication.¹⁵

This publication showed a time difference (Δ) of 9 minutes with a standard deviation (σ) of ± 10 minutes in both intervention groups.

To be able to detect an even smaller time difference of 5 minutes and with a standard deviation of 10 minutes and a drop of percentage of 20% ($\alpha = 0,05$ and $1-\beta = 0,80$) we calculated $n_1=n_2= 75$. A total of 150 patients will be enrolled.

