Exclusion criteria	
 1. Inpatient status 2. Active Congestive Heart Failure Exacerbation 3. Untreated ischemic heart disease 4. Acute exacerbation of respiratory disorders, including COPD and asthma 5. Emergent procedures 6. Pregnancy 7. Previous enrollment in this study 8. Inability to provide informed consent 9. Additional medical testing planned for the same day 10. History of allergic reaction to Propofol 11. Tracheostomy 12. Supra-glottic or sub-glottic tumor 13. Gastrointestinal tract obstruction or delayed transit (including delayed gastric emptying, gastric bezoar, achalasia, toxic megacolon). 14. Prisoners 15. Unable to fit SuperNoVa
Study Procedures	
Pretreatment Evaluation	Candidates will be assessed if the SuperNova fit is difficult or impossible
On-Study Visits	N/A
Follow-up Visits	N/A
End of Study Visit	Subjects will be assessed in PACU before he or she is discharged
Brief Analysis Plan	
Based on the literature, the elapsed time from anesthesia induction to the first airway intervention was 19 ± 10 min in the Mask group ($n=63$) vs. 10 ± 12 min in the Control group ($n=73$, $P < 0.001$)¹⁵. For sample size calculation we used the standard sample size calculation equation¹⁶:
 $n = \frac{2(Z_{\alpha} + Z_{1-\beta})^2 \sigma^2}{\Delta^2}$ 
σ = variation of the measurement Δ = difference to be detected
 
σ and Δ are based on the outcome values from previous publication.¹⁵ This publication showed a time difference (Δ) of 9 minutes with a standard deviation (σ) of ± 10 minutes in both intervention groups. To be able to detect an even smaller time difference of 5 minutes and with a standard deviation of 10 minutes and a drop of percentage of 20% ($\alpha = 0,05$ and $1-\beta = 0,80$) we calculated $n_1=n_2= 75$. A total of 150 patients will be enrolled.

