4.1. Randomization

A random number generator program will be used to assign sequential qualified study cases to control group (N = 69) or SuperNO₂VA™EtCO₂ group (N = 69) before collection of additional demographic information and before anesthetic and surgical care. After study group assignment, baseline data will be collected, including age, gender, height, weight, and BMI.

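### The sample size does not deliver the stated 80% power for 5 minutes: the control SD is misquoted, 75 per arm does not cover 20% dropout, and another section gives 69 per arm

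*Combined protocol and SAP*

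**What the plan says.** The sample size is justified in Section 10.1 (Sample Size Determination) and, in nearly the same words, in the Brief Analysis Plan of the Summary Table.

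- **Target.** The plan uses the usual normal-approximation formula for two means with α 0.05 and power 0.80. The aim is stated as "To be able to detect an even smaller time difference of 5 minutes"; the earlier trial had observed 9 minutes.
- **Standard deviation.** Section 10.1 says the earlier trial showed "10 minutes in both intervention groups", and the calculation uses 10. The Brief Analysis Plan first reports that trial as 19 ± 10 min in the mask group (n=63) and "10 ± 12 min in the Control group" (n=73), then repeats the statement that the SD was 10 in both.
- **Dropout.** The calculation allows for "a drop of percentage of 20"%. The inflation step is not shown. The result is 75 per arm, 150 in total.
- **Allocation.** Section 4.1 (Randomization) assigns cases to a "control group (N = 69") and a device group of the same size, 138 in total.

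**The concern.** Three elements of the calculation do not fit together: the SD differs from the source figures the plan itself prints, 75 looks too small for the stated dropout allowance, and the randomization section uses a different arm size.

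The claim of 80% power for a 5-minute difference is the stated justification for the trial's size. If true power is nearer 70%, the chance of missing a real 5-minute effect is about 30% rather than 20%, and a null result would be read against a power the design did not have. The 75 versus 69 conflict also leaves two possible points at which enrolment is complete.

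**Working it through.** **Inputs.** From Section 10.1: Δ = 5 min, σ = 10 min, α = 0.05, power 0.80, dropout 20%, 75 per arm. From the Brief Analysis Plan: SD 10 (n=63) and SD 12 (n=73). From Section 4.1: 69 per arm. The plan does not say whether α is one- or two-sided. Two-sided is assumed, because one-sided α needs only 50 evaluable per arm (60 to 63 after inflation) and cannot give 75.

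**1. The plan's own figure.**

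n = 2(z₁₋α/₂ + z₁₋β)²σ²/Δ² = 2(1.960 + 0.842)² × 100/25 = 62.8, so 63 evaluable per arm.

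- Multiplying by 1.2: 62.8 × 1.2 = 75.3, which matches the stated 75.
- Dividing by the fraction retained: 62.8/0.8 = 78.5, so 79 per arm.

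The ×1.2 step is an inference, since the plan shows none. The shortfall does not depend on it: 75 × 0.8 = 60, which is below 63 however 75 was obtained.

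**2. The SD implied by the quoted source.**

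Pooled SD = √[(62 × 10² + 72 × 12²)/134] = √(16,568/134) = 11.12.

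Weighting the two arms equally, as in a 1:1 trial, gives √[(100 + 144)/2] = 11.05. Evaluable n for 80% power at 5 minutes becomes 78 per arm (SD 11.12) or 77 (SD 11.05), not 63.

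**3. Evaluable patients after 20% loss.** 75 × 0.8 = 60; 69 × 0.8 = 55.2, taken as 55.

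**4. Power for 5 minutes.** Power ≈ Φ(Δ/[σ√(2/n)] − 1.960), with the t-test value (noncentral t) in brackets.

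| Evaluable per arm | SD 10 | SD 11.12 |
|---|---|---|
| 75 (no dropout) | 86.5% (86.0%) | 78.6% (78.1%) |
| 60 (75 less 20%) | 78.2% (77.5%) | 69.3% (68.5%) |
| 55 (69 less 20%) | 74.6% (73.8%) | 65.5% (64.7%) |

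For example, at n = 60 and SD 11.12: 11.12 × √(2/60) = 2.03; 5/2.03 = 2.46; Φ(2.46 − 1.96) = 69%. With SD 11.05 the same cell is 69.8% (69.1%).

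**5. Difference detectable with 80% power at 60 per arm.** 2.802 × σ × √(2/60) = 5.1 min at SD 10 and 5.7 min at SD 11.12.

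**The case against.** The strongest reply is that no single defect does much harm at 75 per arm. Inflating incorrectly at SD 10 costs about 2 points (78.2%), and the larger SD with no dropout also costs only 1 to 2 points (78.6%). This is correct: the drop to about 69% comes from the two acting together. But the plan assumes 20% dropout and prints the SD of 12 itself, so the combined case follows directly from its own inputs.

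Second, 5 minutes is deliberately cautious. At the source's 9-minute difference with SDs 10 and 12, power is about 99% even with 55 to 60 evaluable per arm. That is worth knowing, and it means the trial is not underpowered for an effect of the size seen before. It does not support a claim that the plan makes at 5 minutes.

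Third, 69 may be a leftover. It appears only in Section 4.1, whereas 150 in total stands in the Summary Table and Section 10.1, and randomization in groups of ten (Section 5.2) fits 150 but not 138. This makes 75 the likelier intention, so the 55-per-arm row is conditional on Section 4.1 being followed. Section 4.1 is nevertheless the text that governs allocation and should agree.

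Finally, the choice between pooled SD 11.12 and equal-weight SD 11.05, or between normal and t calculations, moves power at 60 per arm only between 68.5% and 69.8%.

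**Conclusion.** The concern holds and must be fixed. Under the plan's own 20% dropout, 75 per arm leaves 60 evaluable. Power for 5 minutes is then 78% with the assumed SD of 10 and about 69% with the SDs the plan quotes from its source, against a stated 80%. If 69 per arm is followed, the figures are about 75% and 65%. The statement that the source SD was 10 in both groups is contradicted by the Summary Table, and 69 per arm is contradicted by the 150 total.

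These figures assume a two-sided 0.05 test of means, 1:1 allocation, dropout spread equally over the arms, and a time to first airway intervention for every evaluable patient. How patients who need no intervention are analysed is a separate matter, as is the interim trigger of 62 patients in the Data Safety Monitoring section.

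**What to change.** Keep 150 patients and correct the text.

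- **Section 10.1 and the Brief Analysis Plan.** Report the source SDs as 10 (mask) and 12 (control), pooled 11.1, and delete the statement that the SD was 10 in both. State that α is two-sided, if that is what was intended. State that 75 per arm leaves 60 evaluable after 20% dropout, giving about 69% power for 5 minutes or, equivalently, 80% power for about 5.7 minutes.
- **Section 4.1.** Change 69 to 75 for both groups.

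This changes wording only and adds no patients; the price is a less favourable stated power. If the sponsor prefers to keep 80% power at 5 minutes with the source SDs and 20% dropout, the size would be 78/0.8 = 97.5, so 98 per arm (196 in total).
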